### JHM IRB - eForm A – Protocol

• Use the section headings to write the JHM IRB eForm A, inserting the appropriate material in each. If a section is not applicable, leave heading in and insert N/A.

• When submitting JHM IRB eForm A (new or revised), enter the date submitted to the field at the top of JHM IRB eForm A.

# **Open Label Peanut Oral Immunotherapy in Children: IMPACT Follow Up Study (IND #17784)**

# 1. Abstract

This application is being submitted as a follow-up to Protocol NA\_00077852 "Oral Immunotherapy for Induction of Tolerance in Peanut Allergic Children." The "IMPACT" protocol was a double-blind, placebo-controlled study of peanut oral immunotherapy in children 12-48 months of age. As part of the IMPACT protocol, all participants who received placebo treatment were promised the opportunity to receive open label treatment at the conclusion of the doubleblind phase and initial follow-up. At the time of submitting IMPACT, we did not specify any detailed protocol for the open label crossover treatment, as this is an evolving field, but we are now ready to offer this open label treatment as promised.

There are no specific hypotheses to be tested. The main research questions will focus on the safety and efficacy of the treatment.

#### 2. Objectives

 The primary objectives of this protocol is to provide open label peanut oral immunotherapy (OIT) for those subjects who received placebo treatment in the doubleblind phase of the above noted study and to assess safety, as measured by the incidence of adverse events and the proportion of subjects who discontinue treatment due to adverse events.

Secondary objective will include:

2. Efficacy of the treatment, as defined by an end of treatment oral peanut challenge.

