### 7. Study Statistics

As an open label follow-on study, statistics will be purely descriptive, describing the proportion of subjects achieving desensitization as well as measures of safety.

**Early stopping rules:** Study enrollment and treatment will be suspended pending expedited review of all pertinent data by the IRB and FDA if the following occur:

- Any death.
- More than one severe anaphylactic reaction related to peanut immunotherapy dosing at any stage of the protocol.
- More than three subjects require 2 or more injections of epinephrine to treat one allergic adverse event during peanut OIT dosing.
- More than 3 subjects require epinephrine on 2 or more occasions to treat dosingrelated reaction over the course of the study

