#### 8. Risks

**OIT:** The primary risk of the study is related to the peanut OIT. Previous studies have shown that mild reactions, such as oral pruritus, are very common, while more severe respiratory or systemic reactions occur in less than 1% of doses. The dosing schema to be used on the initial escalation day followed by the build-up phase of immunotherapy is based on previous experience with peanut, egg, milk, and wheat OIT. In addition to acute reactions, 10-20% of treated subjects experience more chronic abdominal pain, which is the most common reason to discontinue treatment. Some of those subjects have eosinophilic esophagitis, which has been estimated to occur in 2-5% of children receiving OIT. Subjects who persist with symptoms consistent with eosinophilic esophagitis such as swallowing difficulty, food impaction, persistent vomiting, abdominal pain, nausea and/or heartburn beyond 4 weeks of OIT avoidance will be referred to GI.

**Oral food challenge:** Since the subjects will have already undergone an End-of-Treatment oral food challenge in the IMPACT study, a baseline food challenge will not be needed to establish a peanut allergy diagnosis. An end-of- treatment challenge will be conducted to determine safe levels of peanut to eat, but the subjects will be substantially desensitized at that time, making reactions less likely overall. However, it is important to recognize that there is still risk of a reaction that could even be severe. Common symptoms may include urticaria, angioedema, nausea, abdominal discomfort, vomiting and/or diarrhea, rhinorrhea, sneezing and/or mild wheezing. The major risks involved include severe breathing difficulties, and rarely, a drop in blood pressure. While a severe outcome is theoretically possible (i.e. death), this has only occurred once in the world in medically supervised oral food challenges. To date the primary investigator has performed more than 5000 oral food challenges without a serious lifethreatening anaphylactic reaction or need for hospitalization

Trained staff will be present to administer study food challenges and a physician will be at the bedside to provide oversight, evaluation, and treatment as needed. The risks of oral food challenges are minimized by the following procedures:

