#### Plan for reporting and collecting adverse events

Reporting will occur as follows:

- i. Toxicity will be graded according to the NCI-CTC for application in adverse event reporting. The NCI-CTC has been reviewed specifically for this protocol and is appropriate for this study population. The purpose of using the NCI-CTC system is to provide standard language to describe toxicities, and to facilitate tabulation and analysis of the data and assessment of the clinical significance of treatmentrelated toxicities. The investigator will try to determine the relationship of toxicity to peanut immunotherapy as not related, possibly related, or definitely related using standard criteria for clinical trials. All grades of toxicity will be noted. Toxicity grades are assigned by the study site to indicate the severity of adverse experiences and toxicities.
- ii. Adverse events, not included in the NCI-CTC listing, should be recorded and graded 1-5 according to the General Grade Definition provided below:

	General Grade Defin	
Grade 1	Mild	Transient or mild discomforts (< 48 hours), no or minimal medical intervention/therapy required, hospitalization not necessary (non-prescription or single-use prescription therapy may be employed to relieve symptoms, e.g., aspirin for simple headache, acetaminophen for post-surgical pain). Examples of anticipated events include: oral/pharyngeal pruritus, localized hives/swelling, skin flushing and/or pruritus, rhinorrhea/sneezing, nasal congestion, occasional cough, throat discomfort, mild abdominal discomfort, nausea or single episode of vomiting.
Grade 2	Moderate	Mild to moderate limitation in activity, some assistance may be needed; no or minimal intervention/therapy required, hospitalization possible. Examples of anticipated events include: systemic hives, throat tightness without hoarseness, persistent cough, wheezing without dyspnea, persistent moderate abdominal pain/cramping/ nausea, repeated vomiting
Grade 3	Severe	Marked limitation in activity, some assistance usually required; medical intervention/therapy required hospitalization possible. Examples of anticipated include: laryngeal edema, throat tightness with hoarseness, wheezing with dyspnea, persistent severe abdominal pain with repetitive vomiting, change in mental status, hypotension

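### Does the primary safety measure, the incidence of adverse events, need a stated unit, window and rule for challenge-day reactions?

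*Combined protocol and SAP*

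**What the plan says.** Section 2 names two primary safety measures: "assess safety, as measured by the incidence of adverse events and the proportion of subjects who discontinue treatment due to adverse events". The second has a per-subject unit. The first has no stated unit, denominator, window, grade or relationship to treatment. Section 7 says the statistics are descriptive only, "describing the proportion of subjects achieving desensitization as well as measures of safety", and defines those measures no further. The Abstract states that no hypotheses are tested.

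Other sections draw the distinctions that Section 2 leaves out:

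- The adverse event plan in Section 8 has the investigator "determine the relationship of toxicity to peanut immunotherapy as not related, possibly related, or definitely related". It records every grade and gives as one purpose of grading "to facilitate tabulation and analysis of the data", together with judging how much treatment-related toxicity matters clinically.
- Three of the four early stopping rules in Section 7 are limited to dosing, for example "More than one severe anaphylactic reaction related to peanut immunotherapy dosing at any stage of the protocol".
- Data and Safety Monitoring treats epinephrine for dosing symptoms as a serious adverse event and reports its location and number of doses to the DSMB.
- Section 2 lists the challenge separately, as the secondary efficacy measure. Section 8 describes the risks of oral immunotherapy (OIT) and of the challenge under separate labels.

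Section 8 gives background risks in two units. Mild reactions are called very common, "while more severe respiratory or systemic reactions occur in less than 1% of doses". By contrast, "10-20% of treated subjects experience more chronic abdominal pain, which is the most common reason to discontinue treatment", and eosinophilic esophagitis is a condition "which has been estimated to occur in 2-5% of children receiving OIT".

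**The concern.** In a descriptive study the chosen summary is the result, so an undefined primary summary deserves a second look. Two things could go wrong.

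First, nothing excludes challenge-day reactions. The challenge goes to 4000 mg cumulative, against a maximum daily dose of 1000 mg, and it is stopped for objective symptoms. A reaction that limits the efficacy result could therefore also be counted as a treatment adverse event. Only children who reach the end of maintenance could contribute one.

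Second, a per-subject incidence depends on how long a child is dosed, and planned exposure varies almost twofold. One figure could not be read against both a per-dose risk and per-subject risks.

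At stake is how readers would interpret the safety result. No error rate or decision rule is involved.

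**Working it through.** **Exposure (Section 4).** The build-up table has 11 steps of 2 weeks, and 11 × 2 = 22 weeks, which reproduces the lower limit given for build-up. With at least 12 weeks of maintenance, the shortest planned course is 22 + 12 = 34 weeks, or 34 × 7 = 238 daily doses. The longest, reading week 64 as study week (52 + 12), is 64 × 7 = 448 doses. The ratio is 448 / 238 = 1.88. The few extra doses on the initial day are ignored and full adherence is assumed.

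**Per-dose against per-subject.** If each dose carries the same independent risk p, the share of subjects with at least one reaction in n doses is 1 − (1 − p)^n. The 1% row is the upper limit of the Section 8 figure for severe reactions; the other rows are assumptions.

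| p (of doses) | n = 238 | n = 448 |
|---|---|---|
| 0.01% | 2.4% | 4.4% |
| 0.1% | 21.2% | 36.1% |
| 0.5% | 69.7% | 89.4% |
| 1% | 90.9% | 98.9% |

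The two units are not interchangeable. But this spread is a property of the units and does not measure an error in the plan. If risk differs between children, each entry is an upper limit for the same mean per-dose risk. If risk falls only in build-up, longer maintenance adds nothing.

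**Challenge reactions added to severe OIT reactions.** If a share q of children react at challenge, independently of earlier reactions, the added incidence is q × (1 − p)^n. The documents give no q. For an assumed q of 5–15% and n = 238:

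- p = 0.01%: 4.9 to 14.6 points
- p = 0.1%: 3.9 to 11.8 points
- p = 0.5%: 1.5 to 4.5 points

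**Challenge reactions added to the measure Section 2 names.** That measure covers adverse events of any grade, and mild reactions are expected to be very common. Take p = 1% of doses for any grade and q = 15%, both assumed:

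- n = 238: 0.15 × 0.99^238 = 0.15 × 0.0914 = 0.0137, about 1.4 points
- n = 448: 0.15 × 0.99^448 = 0.15 × 0.0111 = 0.0017, about 0.2 points

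The incidence is already near its ceiling, so the challenge barely moves it. The larger effects need a different measure (severe reactions only) and a low assumed risk.

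**Can the events be separated?** Each event carries a grade and a rating of its relationship to peanut immunotherapy. The challenge follows maintenance, so its reactions can be identified by date. Separate tables therefore need no new event data. A rate per dose would also need a count of doses taken. Home diaries are reviewed at dosing visits and a dispensing log is kept, but the protocol does not say what the diaries record.

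**The case for a change.** The strongest contrary case is that unit, grade and challenge handling would be chosen after open-label results are seen, with no test to anchor the choice. The expedited reporting rule speaks of events related to the study's experimental procedures, and the challenge is one of those. The purpose given for grading does not specify a table or mention the primary measure. An any-grade, any-cause proportion near its ceiling would also tell readers little without a breakdown by grade.

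Part of this stands. Sections 2 and 7 do not state the unit or window, and no section says how challenge-day events are tabulated. A sentence in Section 7 could say so at little cost.

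The rest is weaker. That challenge reactions would be pooled is an inference from silence, and the protocol's structure points the other way. The per-dose figure in Section 8 is background from previous studies, and no comparison with it is planned. The breakdown by grade is what the adverse event plan already prepares for. A per-dose rate has its own weaknesses: it gives most weight to children who stay on longest, and exposure is partly an outcome, since dose-limiting symptoms at an up-dosing visit lengthen build-up by 2 weeks (14 doses).

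**Conclusion.** No change to the plan is needed. This is missing detail that analysts can be expected to fill sensibly: subjects with at least one adverse event on OIT, by grade and relationship, with challenge-day reactions shown apart. No stated rule gives a wrong result, and no test, sample size or stopping rule depends on the measure. The other primary measure, discontinuation due to adverse events, already has its unit and is largely unaffected.

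On the any-grade measure, counting challenge reactions would add about 1.4 points at 238 doses and 0.2 at 448. Those figures assume a constant, independent 1% any-grade risk per dose and 15% of children reacting at challenge. The effect could reach 14.6 points only for severe reactions at an assumed 0.01% of doses, and only if the analyst pooled events that the records keep apart. This study's actual risks are not in the documents, so neither figure is a forecast. The conclusion would weaken if challenge-day events could not be told from dosing events, but their date and the relationship rating make that unlikely.

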#### 3. Background

Anaphylaxis is a severe, potentially fatal, systemic allergic reaction that occurs suddenly after contact with an allergy-causing substance. Peanut allergy affects 1-2% of US children and is associated with a high risk of life-threatening anaphylaxis. Even more concerning, peanut is the allergen most commonly associated with death and near-death following food-induced anaphylaxis and is frequently encountered in common food products. Peanut allergy also persists into adulthood in the majority of affected individuals, with less than 25% of peanutallergic children naturally developing tolerance.

Currently, treatment for peanut allergy is limited to dietary avoidance and ready access to selfinjectable epinephrine. However, immunotherapy for food allergy has been evaluated extensively over the last decade with studies focusing on oral, sublingual and epicutaneous immunotherapy to treat peanut, milk and egg allergy. When comparing these forms of immunotherapy for peanut allergy, oral immunotherapy (OIT) has proven to be the most efficacious to date.

The rationale for this study is that peanut OIT will induce immune modulation resulting in suppression of allergic responses allowing for desensitization to peanut and protection from anaphylaxis. The use of peanut flour for this study is similar to other single allergen OIT studies. The study product will be manufactured by the University of North Carolina. We have selected a dosing strategy based on all available information that is most likely to best balance safety with efficacy.

#### 4. Study Procedures

This study will provide open label peanut OIT, with a maintenance dose of 1000 mg of peanut protein. Treatment will be initiated on a single day in which multiple doses are given. Peanut flour will be given incrementally and increased every 15-30 minutes until a maximum dose of 6 mg peanut protein is given. This visit may take up to 6 hours to complete:

Initial Day Dose Escalation		
Dose #	Peanut Protein (mg)	
1	0.8	
2	1.5	
3	3.0	
4	6.0	

A minimum of 1.5mg must be achieved on the initial dose escalation day. In other studies all subjects have achieved at least 1.5 mg with no more than mild symptoms reaction. After the initial dose escalation day, subjects will return to the research unit the next day for an observed dose administration of the highest tolerated dose from the initial escalation day. Subjects who tolerate 6 mg during initial dose escalation and again on the observation day following initial dose escalation will proceed with dosing per the table below. Subjects who do not reach 6 mg on the initial dose escalation day will require additional up-doing visits to escalate to the 6 mg dose (Example: from 1.5 to 3.0 to 6.0 ) mg before beginning the dose build up schedule described below. Once subjects have tolerated a dose under observation, they will then continue dosing at home with OIT and return to the research unit every 2 weeks for a 1-step dose escalation to a maximum daily dose of 1000 mg (see table below). Subjects may remain on a single-maintenance dose for longer than 2 weeks if necessary. The dosing escalations will be consistent with previous OIT studies. Participants who do not reach the 1000mg dose during the build-up phase may enter the maintenance phase at their highest tolerated dose. Subjects must achieve a minimum of 200mg during the build up to enter the maintenance phase.

Mild symptoms with dosing such as transient nausea, mild abdominal pain, and/or oral pharyngeal pruritus are common and are not considered dose limiting. Dose limiting symptoms include those that do not respond to antihistamine and/or require the use of epinephrine.

Subjects who experience dose limiting symptoms during an up-dosing visit will continue on the previously tolerated dose for an additional 2 weeks. Subjects who experience dose limiting symptoms with a home dose will be seen in the research unit for down-dosing to the last tolerated dose. Subjects will remain on the last tolerated dose for at least 2 weeks before attempting another up-dosing. A subject may attempt a specific dose level 3 separate times before the dose is considered "not tolerated". In that case, the dose previously tolerated will become the maintenance dose and the subject will not attempt additional up-dosing.

Dose Build-Up Schedule				
Dose #	Peanut protein	Interval (weeks)	% Increase	
5	10 mg	2	66%	
6	20 mg	2	100%	
7	30 mg	2	66%	
8	50 mg	2	60%	
9	75 mg	2	33%	
10	125 mg	2	60%	
11	200 mg	2	62.5%	
12	300 mg	2	33%	
13	500 mg	2	60%	
14	750 mg	2	50%	
15	1000 mg	2	25%	

Consent will be obtained at the last visit in IMPACT Study. For subjects who have already completed the last visit of that protocol and/or families who request additional time to review the consent, consent will be obtained at the 1st visit in the Pediatric Clinical Research Unit prior to

any research specific procedures. The study will be explained in age appropriate terms to the participants and they will be given the opportunity to ask questions. Some of the older subjects may have some context to comprehend the assent process. The assent process will be documented in the clinical note.

At each dosing visit, the following procedures will be performed prior to dose administration:

- Vital signs
- Review of adverse events including any accidental exposure to peanut
- Review of concomitant medications
- Review of home dosing diaries
- Physical exam
- Peak flow

The build-up phase will comprise up to 22-52 weeks. Subjects will then enter the Maintenance phase and will continue on daily OIT at the maximum tolerated dose established during the Build-up phase. The Maintenance phase will consist of at least 12 weeks and may continue as long as through week 64. Subjects will be seen every 6-8 weeks during the Maintenance phase. The window between maintenance visits may be extended to longer than 6-8 weeks if necessary. At the end of the Maintenance phase, subjects will undergo an open peanut oral food challenge to a maximum of 4000 mg of peanut protein using the following dosing regimen:

Dose #	Peanut Protein (mg)	Cumulative Dose (mg)
1	100	100
2	300	400
3	600	1000
4	1000	2000
5	2000	4000

After this food challenge all participants will be given individualized guidelines for the introduction of peanut into their diet based on the outcome of the open peanut challenge.

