# 5. Inclusion/Exclusion Criteria

#### Inclusion:

- 1. Parent guardian must be able to understand and provide informed consent
- 2. Subjects enrolled in Protocol NA\_00077852 "Oral Immunotherapy for Induction of Tolerance in Peanut Allergic Children" who meet at least one of the following criteria:
- a. a reaction to a cumulative dose of ≤1000 mg of peanut protein during the EndofTreatment food challenge
- b. subjects determined to be assigned to the placebo cohort **Exclusion**:

- 1. Inability or unwillingness of a parent guardian to give written informed consent or comply with study protocol
- 2. History of severe anaphylaxis to peanut, defined by severe hypoxia, hypotension, neurological compromise, confusion, cardiovascular collapse, or loss of consciousness
- 3. Significant chronic disease (other than asthma, rhinitis, or atopic dermatitis) requiring therapy; e.g., heart disease or cystic fibrosis which is judged by the investigator to have potential impact on study outcomes or safety.
- 4. Severe or poorly controlled atopic dermatitis per investigator's discretion
- 5. Past or current history of eosinophilic gastrointestinal disease
- 6. Diagnosis of asthma that meets any of the following criteria:
  - Uncontrolled asthma (as per Global Initiative for Asthma [GINA] latest guidelines)
  - History of 2 or more systemic corticosteroid courses in the last year or 1 systemic course within the 3 previous months prior to visit 1 for treating wheezing
  - Prior intubation/mechanical ventilation for asthma
- 7. Currently receiving β-blocking agents, angiotensin-converting enzyme inhibitors, angiotensin-receptor blockers, calcium channel blockers or tricyclic antidepressant therapy.
- 8. Current participation in another clinical trial or participation in another clinical trial in the last 90 days

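### Section 4's dose-adjustment and re-attempt rules make no exception for a reaction that meets the protocol's own Exclusion 2 definition of severe anaphylaxis

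*Combined protocol and SAP*

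**What the plan says.** Section 4 defines the reactions that limit dosing: "Dose limiting symptoms include those that do not respond to antihistamine and/or require the use of epinephrine". It then gives three instructions on what follows.

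- Reaction at a clinic up-dosing visit: "Subjects who experience dose limiting symptoms during an up-dosing visit will continue on the previously tolerated dose for an additional 2 weeks".
- Reaction at home: "Subjects who experience dose limiting symptoms with a home dose will be seen in the research unit for down-dosing to the last tolerated dose". The child then stays at that dose for at least 2 weeks before up-dosing is tried again.
- Repeat attempts: "A subject may attempt a specific dose level 3 separate times before the dose is considered" not tolerated.

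For the initial escalation day, Section 4 says that "subjects will return to the research unit the next day for an observed dose administration of the highest tolerated dose" reached that day.

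Section 5 excludes from entry any child with this history (Exclusion 2): "History of severe anaphylaxis to peanut, defined by severe hypoxia, hypotension, neurological compromise, confusion, cardiovascular collapse, or loss of consciousness".

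Section 7 suspends enrollment and treatment pending IRB and FDA review on any of four triggers. The one closest to this point is: "More than one severe anaphylactic reaction related to peanut immunotherapy dosing at any stage of the protocol".

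In the adverse event plan in Section 8, hypotension and altered mental status are examples of Grade 3, and related events of Grade 3 or above go to the DSMB and IRB quickly. Under Data and Safety Monitoring, epinephrine for a dosing reaction is a serious adverse event reported to the DSMB, and the Principal Investigator decides what to do about the individual participant.

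**The concern.** The protocol judges that a child with past severe anaphylaxis to peanut should not start OIT. If the same kind of reaction occurs during OIT, the only text that says what dose comes next is the routine adjustment text, which tells staff to keep dosing at a lower level and allows the level to be tried again. The participants are peanut-allergic children who take most doses at home.

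What is at stake is the safety of the first child who has such a reaction, before any study-wide rule can act. The effect on the reported proportion discontinuing because of adverse events, part of the primary objective, would be small and is not the ground for this point.

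**Working it through.** The plan states no figure to reproduce: there is no sample size, and the statistics are descriptive. The check is a reading of the rules side by side, with three short counts.

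**Step 1. Does an Exclusion 2 reaction fall inside the Section 4 rules?** The definition sets a floor: no response to antihistamine, or epinephrine needed, or both. A dosing reaction with hypotension or loss of consciousness that is treated with epinephrine meets it. Neither the definition nor the three follow-on instructions has a ceiling or an exception. The next-day dose after the initial escalation day has none either. A child who reacts in this way at 6.0 mg after tolerating 3.0 mg is scheduled for 3.0 mg the next day.

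**Step 2. What further dosing does the text permit?**
- Daily doses at the held or reduced level: 2 weeks × 7 days = 14 after a clinic reaction, and at least 14 after a home reaction.
- Further attempts at the level that caused the reaction: 3 allowed − 1 used = 2.

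**Step 3. Does a study-wide rule intervene?** The severe-anaphylaxis trigger is a count above 1. The first reaction gives a count of 1, so it does not trigger. A second gives 2 and triggers, whether in the same child or another, because the rule counts reactions and not subjects. The two epinephrine triggers each need more than three subjects, that is, at least 4, so one child's event alone does not meet them. The remaining trigger is a death. A first non-fatal reaction therefore suspends nothing on its own.

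The same rule limits Step 2. If a re-attempt produces another severe anaphylactic reaction, treatment is suspended before the last permitted attempt.

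**Step 4. Does an individual-level rule intervene?**
- Grading and expedited reporting settle who is told, not whether the child is dosed the next day.
- The minimums of 1.5 mg on the first day and 200 mg to enter maintenance limit continuation by dose tolerated. They do not refer to severity.
- Principal Investigator discretion allows OIT to be stopped but gives no criterion for doing so.

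For a first reaction of this kind, the written instruction is to continue. Against it stands only a discretion with no stated threshold.

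**The case against.** The strongest reply is that stopping an individual child is already provided for. The Principal Investigator decides the course of action, with serious adverse event reporting to the DSMB and expedited reporting of related Grade 3 and higher events. On this view Section 4 governs dose level, the monitoring section governs the participant, and no experienced allergist would read the adjustment text as covering collapse.

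Much of this stands. A reader might infer that the protocol compels continued dosing after severe anaphylaxis; the documents do not support that, because the discretion to stop is there. What remains is that Section 4 is specific and directive, the discretion is general, and nothing says which prevails. If every investigator would stop, writing it down changes no one's practice.

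A reader might also extend the point to eosinophilic esophagitis, since Exclusion 5 bars "Past or current history of eosinophilic gastrointestinal disease" and no dosing rule follows a new diagnosis. The documents do not support saying that such a child may stay on OIT under the written rules. Section 8 makes GI referral follow symptoms that persist beyond 4 weeks off OIT, and no rule restarts dosing. The protocol lacks only a restart rule, and permanent discontinuation after that diagnosis is open to clinical debate. The 2-5% rate in Section 8 is how often the condition occurs, not how often a diagnosed child is dosed again.

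Finally, it can be said that the fix draws its line at Exclusion 2 and leaves other severe reactions, such as laryngeal edema, under the three-attempt rule. That is true. The line is the sponsor's own entry criterion, and the sponsor could set a wider one.

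**Conclusion.** The point holds for severe reactions: Section 4 gives a directive dosing rule with no exception for a reaction that the protocol itself treats as disqualifying at entry. It should be corrected on patient-safety grounds.

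Its size is limited to what the text permits: 14 or more further daily doses and up to 2 re-attempts in the affected child, subject to suspension after a second severe reaction. No rate of Exclusion 2 reactions is given, so neither an expected number of children nor a probability of harm is claimed. Comparing adjacent steps in the build-up table would describe the dose reduction after any dose limiting reaction and would not measure this gap.

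The conclusion rests on two assumptions: that the Principal Investigator has not used the discretion to stop, and that a severe anaphylactic reaction in Section 7, which is not defined there, means the same as in Exclusion 2. Eosinophilic esophagitis is not part of the finding.

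**What to change.** Add one paragraph to Section 4, for example: *The next-day dose, hold, down-dose and re-attempt rules do not apply to a subject who has an OIT-related reaction with any feature listed in Exclusion 2. OIT is discontinued in that subject, no end-of-treatment challenge is performed, and the event is counted as discontinuation due to an adverse event.* The three-attempt rule and Principal Investigator discretion stay as they are for all other dose limiting symptoms.

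The change adds no dosing visits. A rare child loses treatment that might have been tolerated at a lower dose and contributes no challenge result to the secondary efficacy outcome. The proportion discontinuing because of adverse events may rise slightly. Because Exclusion 2 names hypotension without a threshold, the sponsor may wish to define one.

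As a separate, optional clarification, the protocol could say whether and how OIT may restart after the avoidance period in Section 8 when eosinophilic esophagitis is confirmed.

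### Do the percentage increases that disagree with the mg doses in the build-up table call for a change to the plan?

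*Combined protocol and SAP*

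**What the plan says.** Section 4 (Study Procedures) of the combined protocol and SAP describes the build-up in words and then in a table headed "Dose Build-Up Schedule".

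- **Starting point:** "Subjects who tolerate 6 mg during initial dose escalation and again on the observation day following initial dose escalation will proceed with dosing" according to the table.
- **Progression:** participants dose at home and "return to the research unit every 2 weeks for a 1-step dose escalation to a maximum daily dose of 1000 mg".
- **Threshold:** "Subjects must achieve a minimum of 200mg during the build up to enter the maintenance phase".
- **Duration:** "The build-up phase will comprise up to 22-52 weeks".

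Each table row gives a dose number, the mg of peanut protein, the interval in weeks and a percentage increase. The row for dose 11, for example, reads "11 200 mg 2 62.5" (percent). The documents do not define the percentage beyond its column heading.

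**The concern.** A percentage increase beside a list of doses has an obvious meaning: the step divided by the dose before it. On that reading most of the printed entries do not follow from the mg figures in the same table.

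The column is also inconsistent within itself. Steps that multiply the dose by 1.5 are labelled 66% (20 to 30 mg), 33% (50 to 75 mg and 200 to 300 mg) and 50% (500 to 750 mg). Equal ratios with unequal labels cannot come from one formula applied to consecutive doses.

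This is worth checking because the table is the working schedule of a paediatric study with safety in its primary objective (Section 2). Two columns that disagree could mean that two schedules had been merged, or that a dose had been mistyped. Either would bear on what participants receive. A lesser possibility is that someone judging the pace of escalation from the percentages would be misled.

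**Working it through.** **Inputs.** All come from Section 4: 6 mg as the dose before dose 5, and doses 5 to 15 as listed in the table.

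**Formula.** Increase = 100 × (new − previous) / previous. A row counts as agreeing if it is within 1 point, so 66 for 66.7 is accepted.

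| Dose | Step (mg) | Printed % | Computed % | Printed − computed |
|---|---|---|---|---|
| 5 | 6 to 10 | 66 | 66.7 | −0.7 |
| 6 | 10 to 20 | 100 | 100 | 0 |
| 7 | 20 to 30 | 66 | 50 | +16 |
| 8 | 30 to 50 | 60 | 66.7 | −6.7 |
| 9 | 50 to 75 | 33 | 50 | −17 |
| 10 | 75 to 125 | 60 | 66.7 | −6.7 |
| 11 | 125 to 200 | 62.5 | 60 | +2.5 |
| 12 | 200 to 300 | 33 | 50 | −17 |
| 13 | 300 to 500 | 60 | 66.7 | −6.7 |
| 14 | 500 to 750 | 50 | 50 | 0 |
| 15 | 750 to 1000 | 25 | 33.3 | −8.3 |

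Three rows agree (doses 5, 6 and 14) and eight do not: six printed lower and two printed higher.

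**Could another definition explain the column?** The number of the 11 rows reproduced by each alternative is:

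- previous / new: 5 (doses 7, 8, 10, 11, 13; for example 125/200 = 62.5%)
- step / new: 3 (doses 9, 12, 15; for example 250/1000 = 25%)
- increase to the next dose, as if the column had slipped a row: 2
- step / midpoint: 0

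None fits throughout. However, every entry can be rebuilt from its own row's dose and the dose above it. Three rows follow the ordinary definition, five follow previous/new and three follow step/new (3 + 5 + 3 = 11). That pattern is what results when one list of doses is put through three different formulas. A second set of doses would not be expected to produce it.

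**Is there a sign of a second schedule?** The 6, 200 and 1000 mg points named in the text all stand in the mg columns of the section's dose tables. Eleven steps of 2 weeks give 11 × 2 = 22 weeks, the lower figure stated for the build-up phase. Applying the printed percentages as a chain from 6 mg gives 6 × 1.66 × 2 × 1.66 × 1.60 × 1.33 × 1.60 × 1.625 × 1.33 × 1.60 × 1.50 × 1.25 ≈ 730 mg. That is not the 1000 mg in the text, so the percentages do not describe a rival route to the stated endpoint.

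**Does anything use the percentages?**

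- Section 4 sets the start, the ceiling and the minimum for maintenance in mg. Its rules for repeat attempts and down-dosing refer to a dose level or to the dose last tolerated.
- The early stopping rules in Section 7 count deaths, severe anaphylactic reactions and epinephrine use.
- The analysis in Section 7 describes the proportion desensitized and measures of safety.

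None of these takes a percentage increase as input.

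**Overall size.** The printed mean is 615.5/11 = 56.0% and the computed mean is 660/11 = 60.0%, a gap of 4 points.

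**The case for a change.** The best case for acting is that this column is the only place where the documents express relative step size, and that its departures lean one way. Taking the mg doses as the reference, it shows three steps below 50% where the doses give one, and three at 66% or more where the doses give five. From 200 to 1000 mg the printed mean is (33 + 60 + 50 + 25)/4 = 42%, against (50 + 66.7 + 50 + 33.3)/4 = 50%. A reader weighing the claim in Section 3 (Background) that the dosing balances safety and efficacy might look at these figures and find the escalation gentler than the doses imply. Correcting one column would cost almost nothing.

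Part of this stands. The discrepancy is genuine, nothing elsewhere in the documents corrects it, and on balance the printed figures are lower. Three things limit it.

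- **The contrast depends on the steps chosen.** For the seven steps from 6 to 200 mg the means are 447.5/7 = 63.9% printed and 460/7 = 65.7% computed, under 2 points apart. One of the larger departures, +16 points at 30 mg, runs the other way.
- **The mg doses are in the same rows.** Anyone assessing the escalation can see the actual step from one row to the next.
- **The plan does not rest its justification on the percentages.** Sections 3, 4 and 8 appeal to available information, earlier studies and previous experience with oral immunotherapy. That a reader was or would be misled is an inference which the documents do not show.

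Calling the entries understatements also assumes that the mg column is the correct one. The neutral description is that the two columns disagree.

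**Conclusion.** The arithmetic criticism is correct, but no change to the plan follows from it. The two columns disagree in 8 of 11 rows (9 if 66% for 66.7% is also counted), by 2.5 to 17 points. They need to be reconciled against the source schedule as a matter of copy-editing. That would leave the conduct of the study, its endpoints, stopping rules and descriptive analysis as they are, because none of them draws on the percentages.

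This conclusion rests on three points: 6 mg is the dose before dose 5; staff dose from the mg entries, as the wording of Section 4 implies; and there is no second mg schedule, of which the documents give no sign. If the source schedule showed different mg doses, the matter would no longer be clerical. Nothing here says which dose or step size is right.
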